The primary aim of the proposed study is to evaluate the change in global CBF with ACZ, so the primary outcome is the change in global CBF after 24 weeks relative to pre-treatment baseline. Based on the preliminary data, we expect to see a 15% difference between the ACZ treatment and placebo groups on the improvement in global cerebral perfusion with standard deviation (SD) of 30%. We ran Monte Carlo simulations under a linear mixed effect model (same model as planned for analysis) and calculated a needed total sample size of n=50 to detect a group difference of 0.5 SD at the 24 weeks (phase 1) assuming a within-subject correlation of 0.5, a significance level of 0.05, and 90% power. We hypothesize a similar group difference in phase 2 (ACZ-ACZ group would not change between weeks 24 and 48 but delayed-start group would improve) and similar power to detect this effect. With 50 patients, for Aim 1.2, we will have 80% power to detect an average correlation as low as 0.39 between CBF and MD or FA. Considering a dropout rate of 18%, we need to recruit 60 participants. Aims 2 are mainly exploratory and parameters derived from this study will be used to help design future larger scale confirmatory studies.

All analyses will be intent-to-treat. To summarize the data, descriptive statistics will be used. Demographics and baseline characteristics at randomization will be summarized for each treatment arm. Generalized linear mixed models will be used to analyze all outcomes and will include treatment group and time, group-by-time interaction, and disease duration (stratifying variable) as covariates, and a random intercept to account for within-patient correlation.

For the primary outcome, we will focus on comparing the treatment groups in phase 1. A linear mixed model will be used to compare the estimated change in global CBF between baseline and week 24 in the ACZ and delayed-start groups. A secondary analysis will study ACZ treatment effect on CBF in different regions by treating regions as clusters in the linear mixed model. If normality of CBF outcome does not hold, an appropriate transformation or different outcome distribution will be used.

For the secondary endpoint at 48 weeks (phase 2), a similar mixed model will be used to compare changes in global CBF between weeks 24 and 48 weeks in the early-start and delayed-start groups. The model will include the same terms as for phase 1.

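### The stated 90% power with 50 patients does not follow from the plan's own inputs: the baseline-to-week-24 contrast has about 41-42% power with categorical time and about 70-72% in the most favourable variant of that contrast tried

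*Combined protocol and SAP*

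**What the plan says.** Section 11 makes the change in global CBF from baseline to week 24 the primary outcome. It expects a 15% difference between ACZ and placebo in the "improvement in global cerebral perfusion with standard deviation (SD) of 30"%, which is 0.5 SD. From Monte Carlo simulation under the model planned for analysis, the sponsor "calculated a needed total sample size of n=50 to detect a group difference of 0.5 SD at the 24 weeks (phase 1"). The settings behind that number are described as "assuming a within-subject correlation of 0.5, a significance level of 0.05, and 90% power". Recruitment is set at 60 to allow for 18% dropout.

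The analysis matches that outcome: "A linear mixed model will be used to compare the estimated change in global CBF between baseline and week 24" in the two arms. The model "will include treatment group and time, group-by-time interaction, and disease duration (stratifying variable) as covariates, and a random intercept".

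For phase 2 the plan hypothesises a group difference of the same order and "similar power to detect this effect". That analysis is to "compare changes in global CBF between weeks 24 and 48 weeks in the early-start and delayed-start groups", and "The model will include the same terms as for phase 1".

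The plan does not state sidedness, allocation ratio, whether time is categorical or continuous, the assumed course of the effect over the visits, or which visits and which coefficient the simulation used. The Stage 3 schedule has pCASL scans every 6 weeks in both phases.

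**The concern.** A 0.5 SD difference in change between two arms of 25 is a modest effect for so few patients. A two-sample comparison at that size falls well short of 90% power. Repeated measurements help only if the model borrows strength from the intermediate visits for the week-24 contrast. A free group-by-time term with categorical time does not do that.

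The 90% figure is the only justification given for the size of the one randomised stage. It implies a 10% chance of missing a true 15-point effect. If the real chance is nearer 60%, a non-significant week-24 result would be read as evidence against a 15-point effect when it is not. The Rationale for Study Design also says that results will inform the power calculation for a larger trial, so the true precision of this stage matters there.

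**Working it through.** **Inputs from section 11:** total n = 50; difference 15 points; SD 30 points; within-subject correlation ρ = 0.5; α = 0.05; random-intercept model, hence equal correlation between all visits.

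**Assumptions not in the plan:** 1:1 allocation (25 per arm), two-sided test, complete data, phase-1 visits at weeks 0, 6, 12, 18 and 24. One-sided results are also given.

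**Step 1: SD of the change.** Var(change) = 2(1 − ρ)SD² = 2 × 0.5 × SD² = SD². The standardised effect is therefore 15/30 = 0.5 whether the 30% is the SD of CBF or of its change.

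**Step 2: categorical time.** SE = √(2/25) = 0.283 SD, so effect/SE = 0.5/0.283 = 1.77. Two-sided power is 41.0% (noncentral t, 48 df) or 42.4% (normal). A Monte Carlo check with estimated variances gave 42.4% (40,000 runs; null rejection 5.1%). The disease-duration main effect does not change this within-patient contrast.

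**Step 3: other readings.** In units of SD:
- Linear time over five visits (phase 1 scaled 0 to 1, Σ(t − t̄)² = 0.625): SE = √(2 × 0.5/(25 × 0.625)) = 0.253.
- Categorical time with a common baseline mean: residual variance 1 − ρ² = 0.75, SE = √(2 × 0.75/25) = 0.245.
- Remaining rows: generalised least squares standard error from (X′V⁻¹X)⁻¹. Piecewise models use nine visits, weeks 0-48, with a knot at week 24.

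Power for 0.5 SD (t to normal); the linear and piecewise rows assume an effect that grows linearly to week 24:

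| Model, n = 50 | SE | Two-sided | One-sided | Detectable at 90%, two-sided (t) |
|---|---|---|---|---|
| Categorical | 0.283 | 41.0-42.4% | 53.9-54.9% | 28.1 points |
| Linear | 0.253 | 49.1-50.7% | 61.9-63.0% | 25.1 |
| Categorical, common baseline | 0.245 | 51.6-53.2% | 64.3-65.4% | 24.3 |
| Piecewise | 0.228 | 57.6-59.4% | 69.9-70.9% | 22.6 |
| Linear, common baseline | 0.219 | 60.9-62.6% | 72.7-73.8% | 21.7 |
| Piecewise, common baseline | 0.196 | 70.4-72.1% | 80.7-81.6% | 19.5 |

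If the effect is instead a step from week 6, linear time gives 34-35% two-sided.

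**Step 4: can another reading rescue the figure?**
- All 60 patients complete: 47.8-49.1% two-sided with categorical time; 78.3-79.7% two-sided and 86.7-87.4% one-sided with piecewise time and common baseline.
- 50 per arm, contrary to the text, with categorical time: 69.7-70.5%.
- 2:1 allocation (33/17), categorical: 37.5-38.8%.
- Correlation needed for 90% with categorical time: 4(1 − ρ)/25 = (0.5/(1.960 + 1.282))² gives ρ ≈ 0.85, against the stated 0.5.
- Patients per arm needed for 90% two-sided (t): 86 categorical, 65 categorical with common baseline, 42 piecewise with common baseline, against 25.

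**Step 5: precision.** Expected 95% interval half-width: 2.011 × 0.283 × 30 = 17.1 points with categorical time; 2.011 × 0.196 × 30 = 11.8 points in the best row.

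**Step 6: phase 2 (change from week 24 to 48), two-sided.** Categorical time has the same SE of 0.283, so 41.0-42.4%. With an effect that evolves linearly, linear time within phase 2 gives 49-51% and the nine-visit piecewise model 58-60%. With a step effect, linear time gives 34-35%. The piecewise model then gives 69-76%, because it misfits the step and its expected estimate overshoots to 0.57-0.60 SD. The highest one-sided value is 84-85%.

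**The case against.** The strongest reply is that 70-72% is not a mathematical ceiling, and that the sponsor may have simulated something more efficient. Normal-approximation figures at n = 50, 1:1, show how:
- An effect constant over weeks 6-24 with a common baseline gives 82.3% two-sided and 89.3% one-sided. Since sidedness is unstated, the latter is close to the stated 90%.
- An effect that rises to week 24 and closes by week 48, with the arms equal at both ends, gives 76.5% two-sided and 85.0% one-sided. With 60 completers these become 83.6% and 90.2%.
- An on/off treatment effect pooled over all nine visits gives about 96% two-sided.

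These figures are arithmetically right, and one of them may explain where 90% came from. But each replaces or constrains the free group-by-time term that the plan specifies, and so answers a different question from the stated contrast. If one was used, the stated power belongs to an analysis other than the planned one and the text still needs correcting.

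Two further points stand in part. The simulation code is not in the documents, so one can say that the figure does not reproduce, but not which single power is true. And this is a pilot whose observed estimates, not its 90% claim, would feed the later trial. That lowers the stakes, but section 11 labels only the Aim 2 analyses as mainly exploratory, and the 90% is attached to the primary aim.

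**Conclusion.** The concern holds. On the plan's own effect, SD, correlation, significance level and sample size, the baseline-to-week-24 contrast does not have 90% power. With 1:1 allocation and two-sided testing it has about 41-42% with categorical time. The most favourable variant of that contrast tried has about 70-72% (81-82% one-sided). The chance of missing a true 15-point effect is therefore about 58-59%, or 28-30% in that best variant, not 10%. With categorical time the expected interval half-width of 17 points exceeds the 15-point target itself. The claim of similar power in phase 2 is likewise unsupported.

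The result rests on equal correlation of 0.5 between visits, complete data and the assumed allocation. Relaxing sidedness or allocation, or counting all 60 patients as completers, does not bring any variant of the planned contrast that was tried to 90%.

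**What to change.** 1. State in section 11 the contrast and coefficient simulated, the assumed effect profile, sidedness, allocation, time coding and visits used. Replace the 90% with the power for 15 points, or the difference detectable at 90% power, under the model adopted. If that is categorical time, two-sided and 1:1, the figures are about 41-42% power for 15 points and 90% power for about 28 points.
2. Recompute phase-2 power separately for the adopted time coding and effect profile, and drop the claim that it is similar.
3. Optional, and not needed to correct the statement: constrain the arms to a common baseline mean, or adjust for baseline global CBF, which is already collected. With categorical time this raises power for 15 points to about 52-53% and lowers the difference detectable at 90% to about 24 points. The constraint would change the planned treatment-group term, so the model description must change with it.

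The cost is one rerun of the simulation and revised protocol wording, plus one model constraint or covariate if item 3 is taken up. No patients, visits or scans are added. The stated power becomes less favourable.

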This stage is designed to determine if daily oral ACZ is tolerated and if tachyphylaxis might occur with long-term use for the specific formulation of oral ACZ that we will utilize. Some authors have reported attenuation of the initial increases in CBF with sustained use or oral ACZ though still showing a persistent increase in cerebral perfusion of between 15% - 20%, when compared to pre-treatment levels (Friberg et al., 1990). In this stage, all subjects will receive baseline pCASL and DSC MRI and will start oral ACZ. Patients will continue on 1000 mg BID dose for 24 consecutive weeks and undergo repeat imaging at predetermined intervals. MRI scans and clinical evaluations will be obtained every 6 weeks with contrast-based scans repeated every 12 weeks. Contrast will be administered every 12 weeks to determine DSC measures of blood flow and whether new lesions have formed. As previously stated, DSC provides measurements of not only CBF but also blood volume (CBV) and transit time of blood (MTT). DSC techniques will provide information that cannot be obtained by using pCASL alone that might be important to determine how blood flow is altered with ACZ.

Stage 3 - Many factors contribute to the formation and evolution of lesions in MS (Cotton et al., 2003; Meier and Guttmann, 2006; Narayana et al., 1998). As much as 60% of MS lesions resolve over six

months while the remainder show evidence of persistent damage (Sahraian et al., 2010). In this stage, all subjects will receive baseline pCASL and DSC MRI and will then be randomized to first receive either daily oral therapy with either "**Treatment A**", extended-release ACZ capsules or "**Treatment B**", placebo capsules for 24 consecutive weeks and undergo repeat imaging at predetermined intervals. MRI scans and clinical evaluations will be obtained every 6 weeks with contrast-based scans repeated every 12 weeks. Contrast will be administered every 12 weeks to determine DSC measures of blood flow and whether new lesions have formed and determine how blood flow is altered with ACZ.

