Visit 1 – Subjects will be randomized to receive Treatment A or Treatment B first for the initial 24 weeks. Subjects will receive MRI brain with and without gadolinium contrast utilizing MRI sequences as detailed in Stage 2a.

Subjects will be contacted by telephone or email monthly to document tolerability and encouraged to report any AE occurring with drug at any point during the study.

Visit 2 – Subjects will receive a complete medical and neurological examination, MSFC & EDSS evaluation as well as patient-reported clinical disability measures (MFIS & MSWS-12) and will be asked questions to ascertain tolerability to daily therapy. All subjects will obtain MRI brain without gadolinium contrast utilizing the sequences described above except for DSC sequence.

Visit 3 – Subjects will receive a complete medical and neurological examination, MSFC & EDSS evaluation as well as patient-reported clinical disability measures (MFIS & MSWS-12) and will be asked questions to ascertain tolerability to daily therapy. All subjects will obtain MRI brain with and without gadolinium contrast utilizing the sequences described above.

Visit 4 – Subjects will receive a complete medical and neurological examination, MSFC & EDSS evaluation as well as patient-reported clinical disability measures (MFIS & MSWS-12) and will be asked questions to ascertain tolerability to daily therapy. All subjects will obtain MRI brain

without gadolinium contrast utilizing the sequences described above except for DSC sequence.

Visit 5 – Subjects will receive a complete medical and neurological examination, MSFC & EDSS evaluation as well as patient-reported clinical disability measures (MFIS & MSWS-12) and will be asked questions to ascertain tolerability to daily therapy. All subjects will obtain MRI brain with and without gadolinium contrast utilizing the sequences described above.

Upon completion of the MRI scan, subjects previously treated with Treatment B will start Treatment A and all subjects will continue on Treatment A for the remaining 24 weeks of the study.

Visit 6 – Subjects will receive a complete medical and neurological examination, MSFC & EDSS evaluation as well as patient-reported clinical disability measures (MFIS & MSWS-12) and will be asked questions to ascertain tolerability to daily therapy. All subjects will obtain MRI brain with and without gadolinium contrast utilizing the sequences described above.

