Secondary outcomes considers repeated measures of MD or FA at different time in different regions. Linear mixed models will be used to evaluate changes in MD and FA from baseline (24 weeks for delayed-start) to 24 weeks (48 weeks for delayed-start) after ACZ therapy. These changes will be compared between regions with and without increased CBF (>15% difference from baseline). Terms in the model will be as for CBF with the addition of increased CBF (yes/no) for the region. Mixed models will also be used to compare MD and FA changes between white matter areas with and without lesions.

Logistic or linear mixed models will be used to evaluate change from baseline to after 24 week ACZ therapy (using phase 1 and phase 2 data) in the tertiary composite change outcome. Models will include the same terms as for analyses of the primary outcome. We will evaluate associations between changes in clinical outcomes and changes in CBF, CBV, and MTT by including each of these variables (one at a time) as a time-varying covariate.

As this trial uses a small sample size, we would not expect statistically significant treatment effects on clinical disability though this exploratory measure should be useful in power calculation for the anticipated larger, randomized clinical trial.

ETHICAL CONSIDERATIONS

Informed Consent

The informed consent form is a method of providing information regarding the trial to a prospective participant and allows for an informed decision about participation in the study. All participants (or their legally acceptable representative) must read, sign, and date a consent form before participating in the study, taking study drug, and/or undergoing any study-specific procedures. If a participant does not speak and read English, the consent materials will be translated into the Spanish.

The informed consent form will be updated or revised whenever important new safety information is available, whenever the protocol is amended, and/or whenever any new information becomes available that may affect a subject's participation in the trial.

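### The phase 1 global CBF model does not adjust for baseline CBF, although every Stage 3 patient is scanned before randomisation

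*Combined protocol and SAP*

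**What the plan says.** All references are to the combined protocol and SAP. Section 11, Sample Size and Statistical Methods, states that "the primary outcome is the change in global CBF after 24 weeks relative to pre-treatment baseline". The models for all outcomes "will include treatment group and time, group-by-time interaction, and disease duration (stratifying variable) as covariates, and a random intercept to account for within-patient correlation". On the primary analysis it adds: "A linear mixed model will be used to compare the estimated change in global CBF between baseline and week 24", for the ACZ and delayed-start groups. It does not say whether the modelled response is raw CBF or change from baseline, or whether time is categorical or linear.

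The sample size comes from simulations under the planned model, "assuming a within-subject correlation of 0.5, a significance level of 0.05, and 90% power". The section does not say which measurements the 0.5 relates.

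Other analyses inherit the term list. For phase 2 (weeks 24 to 48), "The model will include the same terms as for phase 1". For the tertiary composite, "Models will include the same terms as for analyses of the primary outcome".

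On timing, the Stage 3 paragraph of Rationale for Study Design says "all subjects will receive baseline pCASL and DSC MRI and will then be randomized to first receive" ACZ or placebo. The Stage 3 Visit 1 entry in Study Visits and Procedures lists the steps in the other order, starting with "Subjects will be randomized to receive Treatment A or Treatment B first for the initial 24 weeks" and naming the MRI afterwards.

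**The concern.** Randomisation makes the true baseline means equal, but the observed means differ by chance. With a free treatment-group term, the week-24 contrast is the difference between arms in mean change, so the whole chance baseline difference is subtracted from the week-24 difference. Under randomisation only a fraction of it, equal to the correlation, should be. The random intercept does not correct this, because the group term absorbs the baseline difference between arms.

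Validity is not at stake: an unadjusted comparison of mean change between randomised arms is unbiased and does not inflate type I error. What is lost is precision, in a trial that calls its own sample small and is meant to supply parameters for a larger one. The scan that would recover the precision is already scheduled.

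**Working it through.** **Inputs.** From section 11: difference 15%, SD 30% (0.5 SD), correlation 0.5, significance level 0.05, power 90%, n = 50 in total. From the Stage 3 visit table: pCASL at weeks 0, 6, 12, 18 and 24. Assumptions: 1:1 allocation (25 per arm), two-sided normal tests, and a constant correlation ρ between raw visits, which is what a random intercept implies.

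**The plan's own figure.** With categorical time the change has variance 2(1 − ρ) = 1 at ρ = 0.5, in units of the per-visit variance. Per arm, n = 2 × 1 × ((1.960 + 1.282)/0.5)² = 84.1, so 85 per arm and 170 in total. The stated 50 is not reproduced and gives 42% power. This is a separate matter and is used here only as the starting point.

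**Variance of the week-24 contrast, raw CBF as response.** Write it as v × 2/25.

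- Categorical time, planned terms: v = 2(1 − ρ). With a common baseline mean: v = 1 − ρ². The ratio is (1 + ρ)/2, a cut of (1 − ρ)/2.
- Linear time, planned terms (visits coded 0 to 4, sum of squares about the mean 10): v = 16(1 − ρ)/10. With a common baseline mean: v = 16(1 − ρ)/[30 − 100ρ/(1 + 4ρ)].

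| ρ | Categorical v, planned to adjusted | Cut | Linear v, planned to adjusted | Cut |
|---|---|---|---|---|
| 0.3 | 1.40 to 0.91 | 35% | 1.12 to 0.684 | 39% |
| 0.5 | 1.00 to 0.75 | 25% | 0.80 to 0.60 | 25% |
| 0.7 | 0.60 to 0.51 | 15% | 0.48 to 0.415 | 14% |
| 0.8 | 0.40 to 0.36 | 10% | 0.32 to 0.292 | 9% |
| 0.9 | 0.20 to 0.19 | 5% | 0.16 to 0.153 | 4% |

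**Power at ρ = 0.5.**

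- Categorical: the SE falls from √(1.00 × 0.08) = 0.283 to √(0.75 × 0.08) = 0.245, and power rises from 42% to 53%.
- Linear, with an effect that builds linearly: the SE falls from 0.253 to 0.219, and power rises from 51% to 63%.
- Total n for 90% power, rounded up per arm: 170 to 128 (categorical) and 136 to 102 (linear).

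**Power at other correlations, categorical time.** If 30% is the SD of change, planned power is 42% whatever ρ is. Adjusted power is 59% (ρ = 0.3), 48% (0.7), 46% (0.8) and 44% (0.9). If 30% is the per-visit SD, power goes from 32% to 46%, 63% to 70%, 80% to 84%, and 98% to 98%.

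**Change as the response, weeks 6 to 24, baseline CBF as covariate.** In 20,000 simulated trials at ρ = 0.5 the variance fell 24% (categorical; SE 0.2816 to 0.2459) and 29% (linear; 0.2613 to 0.2207). At 0.9 it fell 3.5% and 5%. The mean estimate stayed at 0.499 to 0.501.

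**Dropout.** With 30 per arm, 18% dropout spread evenly over weeks 6 to 24 (assumed) and ρ = 0.5, the cut is 22% (categorical; power 44% to 54%) or 23.5% (linear; 52% to 64%).

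**Type I error.** With variance components estimated and 10,000 trials, rates were 4.3% to 4.8% under the planned terms and 4.3% to 4.9% with a common baseline.

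**The case against.** The strongest objection is to the headline size. Section 11 attaches the 30% SD to improvement in perfusion, most naturally the SD of change, and does not say what the 0.5 correlates. If it is the correlation between changes from baseline, it says nothing about ρ: under constant correlation that value is (1 − ρ)/[2(1 − ρ)] = 0.5 for every ρ. The size would then be known only as a range, 4% to 39% for raw CBF over ρ of 0.3 to 0.9. With 30% as the SD of change, the power gain at ρ = 0.9 is only 42% to 44%. This stands, and the 25% is therefore conditional. The gain is still positive for any ρ below 1.

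The fix is also not cost-free under every coding. With linear time and raw CBF, an effect that does not build linearly distorts the week-24 estimate with or without the fix, and the common baseline moves it. For a true 0.50 SD at ρ = 0.5, the estimate goes from 0.40 to 0.50 if the effect plateaus at week 6, and from 0.40 to 0.35 if it appears only at week 24. That is a property of linear coding and leaves type I error unaffected, but it should be known before choosing the wording.

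Two further points are fair. The phase 1 regional CBF comparison uses the same randomised arms and baseline scan, so the same reasoning could extend to it. Restricting the fix to global CBF is cautious and leaves the regional analysis no worse than planned. Finally, the planned analysis is valid and the trial is a pilot, so this is a refinement and not the repair of an error.

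One objection fails. Using change as the outcome does not already account for baseline, because subtracting baseline is not adjusting for it.

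**Conclusion.** The point holds. Neither the term list nor any other Stage 3 text adjusts for baseline CBF, and the primary contrast loses precision as a result. If 0.5 is the correlation between raw visits and raw CBF is the response, adjustment cuts the variance by 25% under either time coding. If change is the response, the cut is 24% (categorical) or 29% (linear). These sizes rest on equal allocation and constant correlation between visits. The existence of a gain does not depend on which time coding or response the plan intends.

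The change is worth making, but it does not rescue the sample size: at 0.5 the adjusted analysis still needs 128 (categorical) or 102 (linear) patients for 90% power, against the stated 50.

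**What to change.** Keep the planned time coding, but state it and the response, and say which measurements the 0.5 relates. Then adjust within that coding:

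- **Raw CBF as response:** drop the treatment main effect so that both arms share one week-0 mean. Keep time, the group-by-time term or terms, disease duration and the random intercept.
- **Change or percent change as response:** model weeks 6 to 24 with baseline CBF as a covariate and keep the other terms.

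State that the common baseline applies only to the phase 1 global CBF comparison. Otherwise the inheritance wording would carry it into the phase 2, MD/FA and pooled tertiary models, where it does not belong. Phase 2, for example, starts at week 24, after the arms have been treated differently. Align the Visit 1 listing order with the Stage 3 rationale, which puts the baseline scan before randomisation.

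The cost is one or two sentences before unblinding, no new data and at most one degree of freedom. With categorical time the estimated effect does not shift. With linear time and raw CBF, note the sensitivity to a non-linear build-up. Moving from linear to categorical time is a separate decision with its own precision cost and is not part of this change.

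### As a main effect only, disease duration (the stratifying variable) effectively does not adjust the baseline-to-week-24 CBF comparison, nor the week 24 to 48 one

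*Combined protocol and SAP*

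**What the plan says.** Section 11 (Sample Size and Statistical Methods) gives one set of model terms for all outcomes: the models "will include treatment group and time, group-by-time interaction, and disease duration (stratifying variable) as covariates, and a random intercept". It lists no duration-by-time term and no baseline-CBF term.

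For the primary outcome, a linear mixed model is to "compare the estimated change in global CBF between baseline and week 24 in the ACZ and delayed-start groups". The phase 2 comparison of change between weeks 24 and 48 uses the same terms.

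The section does not say outright what the modelled response is. It states that "the primary outcome is the change in global CBF after 24 weeks relative to pre-treatment baseline", which could mean that change is the response. The rest of the wording (estimated change as a model contrast, a random intercept, a within-subject correlation, normality of CBF) fits CBF at each visit better.

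Disease duration is called the stratifying variable here, but the Randomization and Blinding section does not mention stratification.

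**The concern.** Disease duration at entry is one value per patient. As a main effect it raises or lowers all five phase 1 visits of that patient equally, so it subtracts out of any difference between two of them. The plan thus lists an adjustment for the randomisation stratum that the primary contrast hardly receives.

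What is at stake is efficiency. If patients with longer disease respond differently in CBF, that variation stays partly in the residual. Under stratified allocation the standard error is then somewhat larger than the real sampling variation of the estimate. In a comparison of about 50 patients even a little precision is worth having when it costs one model term.

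**Working it through.** **Inputs from Section 11.** The target is "to detect a group difference of 0.5 SD at the 24 weeks (phase 1"), with CBF "with standard deviation (SD) of 30" percent, so 15 points. The calculation is run "assuming a within-subject correlation of 0.5", with "a significance level of 0.05, and 90% power". Recruitment: "Considering a dropout rate of 18%, we need to recruit 60 participants". The Stage 3 schedule has five phase 1 pCASL scans (weeks 0, 6, 12, 18, 24). Assumed here, because not stated: 1:1 allocation (25 per arm) and a two-sided test.

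**The plan's own figure.** The variance of change is 2 × (1 − 0.5) × 30² = 900, so its SD is 30. For the week-24-minus-baseline contrast, n per arm = 2 × (1.960 + 1.282)² × 30²/15² ≈ 84.1, or 85 with the t correction, which is 170 in total. The stated 50 does not reproduce on this contrast; it gives about 42% power. Dropout: 50/0.82 = 60.98, against 60 stated. The sample size is a separate matter. It enters here only as the level from which gains are counted.

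**The cancellation.** Write CBF for patient i at visit t as μ(arm, t) + γ·duration_i + b_i + e_it. Week 24 minus baseline is μ(arm, 24) − μ(arm, 0) + e_i24 − e_i0. Both γ·duration_i and the random intercept are gone. Week 48 minus week 24 gives the same result.

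**Check by simulation, complete data.** REML random-intercept fits, 50 patients, 5 visits, correlation 0.5, and an assumed duration effect on the week-24 change of 0.3 SD per SD of duration (150 runs). The duration main effect moved the estimate by 0.000000 and its standard error by at most 0.000004. Power was 0.393 with and without it.

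**With dropout.** Missing at random, nominal 18%, same assumed effect. The main effect moved the estimate by 0.026 SD on average (0.026 × 30 = 0.8 CBF points) and by at most 0.14 SD (4.2 points). It moved the standard error by at most 0.005 SD (0.15 points). Power was 0.373 without it and 0.380 with it. Monte Carlo error is about 4 points, so these runs cannot resolve a gain of a point or so from any version of the model.

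**Size of the gain from duration-by-time.** Let duration explain a share R² of the variance of change (900), with an effect that grows linearly over the five visits; both are assumptions. The true residual variance is then s = 900(1 − R²)/2. A random-intercept model without duration-by-time pools residuals over all visits and estimates s + 900R² × 0.625/4. Here 0.625 is the sum of squares of (−0.5, −0.25, 0, 0.25, 0.5). The standard error of the contrast is √(residual variance × 2 × 2/25) = √(0.16 × residual variance). Approximate power is Φ(15/SE − 1.96).

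| R² | Residual variance without / with | SE without / with | Power without / with |
|---|---|---|---|
| 0 | 450.0 / 450.0 | 8.49 / 8.49 | 42.4% / 42.4% |
| 0.05 | 434.5 / 427.5 | 8.34 / 8.27 | 43.6% / 44.2% |
| 0.10 | 419.1 / 405.0 | 8.19 / 8.05 | 44.9% / 46.2% |
| 0.25 | 372.7 / 337.5 | 7.72 / 7.35 | 49.3% / 53.2% |

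Simulation of the planned model agrees. Gains were about 0 to 1, 1 to 1.5 and 3 to 6 points at R² of 0.05, 0.10 and 0.25. With balanced strata and R² = 0 the SE was 8.47 both ways. At R² = 0.25 the mean SE without the term was 7.73 against an empirical SD of 7.37; with the term it was 7.34.

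**The case against.** **Change may be the response.** If change from baseline is modelled at weeks 6 to 24, the duration main effect does adjust the phase 1 contrast. In simulation under the assumed association, power went from 0.38 to 0.43 (150 runs). This stands as a possible reading, and it is the reason to state the response. It does not help phase 2: week 48 minus week 24 is still a difference within patients, and the main effect cancels there too.

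**The plan expects incomplete data.** A reader might infer that the duration term does nothing at all. The documents do not support that, because exact cancellation needs complete data and Section 11 expects 18% dropout. The logistic mixed models for the tertiary outcome are also outside the exact result. For the primary comparison the effect under dropout is nonetheless small.

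**No harm is shown.** A reader might infer a biased or invalid primary test. That does not follow: under randomisation the contrast is unbiased without any adjustment. Stratified allocation already gives the estimate most of its precision; in one simulation at R² = 0.25 with balanced strata, the empirical SD was 7.51 without and 7.47 with the interaction. What is left is a standard error that does not credit the stratification.

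**The loss could be overstated.** A reader might multiply the SD of change by √(1 − R²) and infer a large loss of power. At R² = 0.25 that implies a 13.4% smaller SE (1 − √0.75). In the planned model it falls by 4.8% (1 − 7.35/7.72), because the pooled residual never carried the full duration variance.

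**Conclusion.** The point holds as a minor improvement. With CBF at each visit as the response, the duration main effect cancels from the primary contrast when data are complete and has little influence under the expected dropout. The same applies to the week 24 to 48 contrast.

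The consequence is a somewhat conservative standard error if duration is related to CBF change. The gain from correcting it is about 0 to 1 point of power at R² = 0.05, 1 to 1.5 at 0.10, 3 to 6 at 0.25, and nil with no association. The documents give no value for R², so this range is illustrative.

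The figures also assume 25 per arm, a two-sided 0.05 test, the stated SD and correlation, and a duration effect linear in time. The conservative direction rests on allocation being balanced within duration strata, which Section 11 implies but the Randomization and Blinding section does not describe.

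**What to change.** In Section 11, state that the modelled response is global CBF at each visit, and add disease duration-by-time to the phase 1 and phase 2 CBF models, with duration coded as in the randomisation strata. Alternatively, model change from the start of each phase (baseline for phase 1, week 24 for phase 2) with duration as a covariate.

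The cost is a line of text before unblinding and, per duration term, 1 degree of freedom with linear time or 4 with five categorical visits. With 50 × 5 = 250 phase 1 scans that is negligible, and nothing measurable is lost if duration turns out to be unrelated to change.
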